9.1.2 Figure 3. Study Duration

Activity:	Screening & Enrollment	Active Treatment	Total Participant Time in Study
Duration:	1-4 weeks	24 weeks	25-28 weeks

9.1.3 Screening and Enrollment Procedures (1-4 weeks duration)

Once a person has completed the Pre-Screening Interview process and meets basic eligibility criteria, they will either be asked to stay for the Screening Visit or scheduled to come back for the visit (based on staff and candidate's availability). It is expected that the screening and enrollment phase will take approximately 1-4 weeks; however, participants will have 60 days from the date of consent to complete screening and be randomized before being considered a screen failure.

9.1.4 Informed Consent Process

Study procedures and the potential risks and benefits of participating in the trial will be explained by research staff. Staff will be available to answer questions about the consent form and consent quiz while participants are reviewing them. After signing the consent form, participants will be given a copy of the form to keep for their records. The process will take approximately 20-30 minutes.

9.1.5 Locator Form

Participants will complete a locator information form which will be used to contact them to remind them of follow-up visits, as well as to locate participants who may not have attended appointments. When completing this form, participants provide their names, addresses, and telephone numbers as well as contact information for at least two other persons. Permission will also be requested to obtain locating information from additional agencies and publicly accessible databases or search engines including, but not limited to, Medicare/Medicaid and Social Security offices, department of motor vehicles, local jail logs, white pages, and Facebook. Locator information will be reviewed at each visit and updated as needed during the study. The locator

information form will take approximately 5-10 minutes to initially complete and content will be checked at future study visits.

9.1.6 Medical Record Release Form

Participants will complete the form(s) as applicable during screening and throughout the study to grant permission to study staff to review inpatient, outpatient, mental health, and substance use treatment clinic records as needed. The purpose of medical record review at the end of study participation is to document information needed to evaluate secondary outcomes. Specifically, study staff will abstract medical record information to corroborate participants' self-report of information including, but not limited to the following: HIV viral load and CD4 count, liver enzymes, hepatitis B and C serologies, CBC, metabolic panel, INR, utilization of HIV primary care, utilization of HIV and addiction treatment services, and opioid overdose events. Records review/abstraction will occur throughout the study (as needed) and up to 52 weeks post-randomization.

9.1.7 Collection of Biological Specimens

Study staff will collect blood specimens at screening, randomization, 12 weeks, and 24 weeks to confirm eligibility and assess the primary outcome of HIV-1 RNA PCR and secondary outcomes of CD4 count, VACS Index, and hepatotoxicity. CBC, serum creatinine, LFTs (AST, ALT), INR, and HIV-1 RNA blood specimens will be collected during screening. CD4, Hepatitis C, Hepatitis B, and PBMC specimens will be collected and processed only after the participant has been randomized. Study staff will collect urine specimens during screening and at treatment initiation (XR-NTX arm only), safety visit (XR-NTX arm only), and at 4, 8, 12, 16, 20, and 24 weeks to confirm eligibility and assess secondary outcomes and pregnancy. Screening and randomization labs (CD4, HIV-1 RNA, and hepatitis B and C serologies) drawn in the 90 days prior to date of informed consent may be abstracted from participant medical records, when available. Other screening lab tests may be abstracted from medical records if drawn within 30 days prior to the date of informed consent, with the exception of urine specimens, which must be collected by study personnel. Some participating sites may require that copies of some or all lab results collected for study purposes be filed in participants' medical records.

9.1.8 Baseline Assessment

After the enrollment process is complete, study staff will prepare a new data record for the participant and the baseline assessments will be administered either through a computer-assisted data collection instrument or a paper version of the CRF. The baseline assessments are detailed in Section 10.0 and capture participant medical, psychiatric, and drug use history, HIV status and care, quality of life, current health status, and other baseline characteristics. The baseline assessment will take approximately 60-90 minutes to complete.

9.1.9 Randomization

The timing of randomization will follow shortly after baseline assessments and final confirmation of eligibility. Participants will be encouraged to initiate treatment within 28 days of randomization. If a participant is unable to initiate treatment within 28 days, he or she may initiate XR-NTX study drug at any time until week 20 and may initiate TAU at any time during the trial. Initiation of assigned treatment will be tracked.

Participants will be randomized in a 1:1 fashion to either office-based XR-NTX or TAU using a permuted block design with randomly-sized blocks. Randomization will be stratified only by site. Participants who meet DSM-5 criteria for both opioid and alcohol use disorder (16% of CTN-0055 CHOICES pilot study participants) will be included, in addition to participants with OUD, alone.

Concomitant alcohol use disorder will be considered as a potential covariate [31], [127, 128]. Participants need not be abstinent from opioids at the time of randomization.

The randomization procedure will be conducted in a centralized process through the Data and Statistics Center (DSC). Specifically, randomization schedules will be created by the study statistician for each site. The randomization schedules will be of a randomized-block nature to ensure relative equality of assignment across condition across the recruitment period and to prevent the potential for study staff guessing the next assignment, which is heightened when a fixed block-size is used. After the baseline assessment is successfully completed, a designated site study staff member will perform the randomization. Randomization for each participant is done over the internet using the Enrollment Module in Advantage eClinical.

The DSC statistician will review the randomization data on a regular basis to ensure that the scheme is being implemented according to plan. If a participant drops out of the study at any point after randomization, the randomization slot will not be re-allocated to a new participant due to the intent-to-treat nature of the study.

9.2 Treatment Conditions

9.2.1 HIV Usual Care (Both Arms)

All participants will receive comprehensive HIV primary care, case management, addiction counseling, and social support services from HIV clinics as they would regardless of study participation. As part of protocol training, HIV clinic providers will be encouraged to offer ART within 4 weeks of randomization for participants not already prescribed ART. Current guidelines recommend offering ART to all HIV-infected participants, regardless of CD4 count [35]. The schedule of medical care provided will be as deemed appropriate by the treating provider. HIV-infected participants are typically seen at least twice within the first month of initiating ART, and at least every 3 months thereafter for monitoring. Medical visits will not be considered study visits, though they may coincide with study visits. HIV clinic treatment will also include usual addiction counseling services, which are offered as a part of usual care in most large U.S. HIV clinics. As part of protocol training, HIV clinic providers will be asked to refer study participants to existing addiction counseling services in their clinic, as they would do regardless of study participation. Throughout the course of the trial, HIV clinics will be monitored for any potential changes that might occur in standard practice around medical management of HIV infection or addiction treatment services. Throughout study participation, HIV clinic medical visits will be tracked through medical record abstraction, and counseling visits will be tracked through participant self-report (See Section 10, Assessments).

9.2.2 Medical Management (when applicable)

Study clinicians will be trained in medical management (MM). MM is a brief counseling intervention delivered by non-addiction medical providers to improve response to medication-assisted addiction treatments delivered in medical settings [129] [130]. It has augmented care for medication-assisted treatment of alcohol dependence with acamprosate and oral naltrexone in the COMBINE study [131], integration of XR-NTX treatment of alcohol dependence in primary care settings [36], and integration of BUP/NX for treatment of opioid dependence in primary care [132]. Since MM is meant to facilitate medication-assisted addiction treatment, it will be performed only for participants offered medication-assisted treatment in the HIV clinic (e.g., participants with opioid use disorders randomized to XR-NTX and TAU participants receiving clinic-based buprenorphine/naloxone or methadone for opioid use disorder). TAU participants referred for off-site methadone maintenance or buprenorphine/naloxone will not receive MM since medical

oversight is the responsibility of the treating provider. TAU participants who receive non-medication-assisted treatments such as 12-step groups or psychosocial counseling will not receive MM. During brief MM sessions, study clinicians will review recent drug and alcohol use, recommend abstinence, review medication side effects, and encourage adherence to medication-assisted treatment and participation in clinic and/or community support groups.

9.2.3 Clinic-based Extended-Release Naltrexone (XR-NTX)

9.2.3.1 *XR-NTX Detoxification and Induction (0 - 4 weeks duration, during active treatment phase)*

Following randomization, participants assigned to office-based XR-NTX will undergo detoxification and naltrexone induction in accordance with the package insert and published guidelines [133-136]. Participating HIV providers will be trained to manage outpatient detoxification procedures for participants with mild to moderate anticipated opioid withdrawal severity. Provider training reviews a range of detox options outlined in the Manual of Operating Procedures [137, 138]. Participants failing an induction regimen and those with anticipated severe withdrawal may be referred to local detox facilities for medication-assisted inpatient detoxification.

9.2.3.2 *Active Treatment with XR-NTX (Treatment Initiation through Week 20)*

XR-NTX (4cc, ~380mg of naltrexone base) will be administered *approximately* every four weeks (treatment initiation visit and weeks 4, 8, 12, 16, and 20) for an approximate maximum of 6 doses in the form of Vivitrol®, which will be obtained by NIDA or the NIDA contractor for distribution to the sites. Administration of XR-NTX more frequently will require approval by the Lead Investigators and will be provided on a case-by-case basis. XR-NTX will be administered by intramuscular injection to the buttocks (alternating sides monthly) according to the injection preparation and administration procedures specified in the Vivitrol® product package insert. These procedures are designed to minimize the risk of injection site reactions.

9.2.3.3 *Handling of Missed XR-NTX Doses, Lapses, and Relapses*

Use of illicit opioids presents different concerns in the management of participants receiving XR-NTX maintenance, compared to those participants receiving agonist therapy. A participant receiving XR-NTX may miss a scheduled injection and resume opioid use. However, because of the long duration of action of XR-NTX (full blockade out to 5 weeks after the last injection [101]), a grace period of at least 7 days after the scheduled injection can be expected during which repeat XR-NTX injection can be rescheduled without risk of relapse. If the participant misses a scheduled injection and uses opioids during at least two of the seven days following the date of the scheduled injection, relapse will be suspected and the provider will perform a repeat naloxone challenge as described in the Manual of Operating Procedures. If the challenge is negative, XR-NTX administration will be resumed. If positive, then XR-NTX administration would risk precipitating withdrawal. However, because naltrexone blood levels remain and there is partial blockade beyond week 5, vulnerability to relapse may be more gradual, and the possibility of mild or equivocal reactions to naloxone challenge more common. In this instance, a second challenge within 72 hours will be attempted, and, if tolerated, the next injection can be given. Missing a scheduled XR-NTX injection is the most important threat to the success of naltrexone maintenance. In the event that a participant misses a scheduled injection, clinic study staff will contact the participant for follow-up. The goal of these contacts is to re-establish commitment to XR-NTX treatment and schedule the next injection as soon as possible. Participants who miss a scheduled XR-NTX dose but remain abstinent (i.e., return to clinic reporting no opioid use, urine negative for all opioids, and passing naloxone challenge), may be restarted on XR-NTX up to 3 weeks after the scheduled dose.

Among the 9 individuals in the pilot study who had opioid use disorder and were unsuppressed at baseline, 6 (17%) of the 36 subsequent viral load values were missing. In the pilot, viral load was measured monthly, increasing the opportunity for missing data, whereas CTN-0067 collects follow-up viral loads only at 12 and 24 weeks and will likely have fewer missing viral loads. The primary outcome analysis will be carried out using the binary repeated measures of viral load (RMVL) framework of Rose et al., a type of time series model. In theory, time series models can accommodate missing data better than non-longitudinal models by using all non-missing data points. However, this approach assumes that missing data are not informative, that is, that missing values are probably similar to corresponding non-missing values with the same set of other predictors. For substance-use trials, missing at random (MAR) is less likely than missing not at random (MNAR) alternative: if data are missing, it is probably because the participant is unsuppressed. So, for the primary analysis, “unsuppressed” will be substituted for missing suppression status values. Since death is at least as undesirable as lack of suppression, “unsuppressed” will be assigned as a status value for visits subsequent to death. A secondary sensitivity analysis will explore the extent to which trial conclusions need to be changed as the missingness assumption approaches MAR.

9.2.3.4 *Dispensing of XR-NTX*

Study medication (XR-NTX) will be provided by the study at no cost to the participant. XR-NTX will be administered in clinic at the Treatment Initiation Visit and at treatment weeks 4, 8, 12, 16 and 20.

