Long-acting antagonist treatment may provide an alternative to daily agonist therapy for patients with opioid use disorder, though its ability to facilitate closing gaps in HIV treatment retention and outcomes is unknown. Extended-release naltrexone (XR-NTX), a deep muscle injection that lasts 28 days, eliminates the need for daily dosing. XR-NTX improves alcohol dependence treatment adherence and retention when integrated into primary care clinics [36, 37], but has not been tested in people living with HIV who are having difficulty engaging in HIV treatment. XR-NTX may also be preferred by some HIV-infected patients seeking a non-narcotic treatment option and/or once a month dosing.

The CTN-0055 CHOICES pilot study demonstrated the feasibility of extended-release naltrexone (XR-NTX) for treatment of opioid use disorder in HIV primary care at two HIV clinic pilot sites. The CTN-0067 CHOICES scale-up study builds on lessons learned from the pilot and uses the Consolidated Framework for Implementation Research to advance understanding of XR-NTX adoption in HIV primary care settings. CTN-0067 CHOICES scale-up study is conducted in no more than 8 HIV primary care clinics. It is an open-label, randomized, comparative effectiveness trial of office-based XR-NTX for 24 weeks (approximately 6 monthly injections) ($n = 175$) versus treatment as usual (TAU) ($n = 175$) in HIV-infected participants with untreated opioid use disorder and HIV RNA PCR > 200 copies/ml at baseline (**Figure 1**). The *primary outcome* is HIV viral suppression (HIV RNA PCR ≤ 200 copies/mL) at 24 weeks. *Secondary outcomes* include VACS Index, CD4 count, HIV care engagement, and ART adherence mediation. The trial will be powered as a non-inferiority trial because the overall goal of the research is to add to rather than supplant currently available effective treatments. An implementation assessment documents best practices. Each participant will be engaged in the overall study for 25 to 28 weeks, depending on the speed of screening and enrollment procedures.

[figure not shown]

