4.1.1 Figure 2. Conceptual Model

4.2 Naltrexone (NTX) and Extended-Release Naltrexone (XR-NTX)

NTX is a potent opioid antagonist with high affinity for the mu-opioid receptor. In the U.S., it is approved for use in treating opioid dependence and alcohol dependence. It is highly efficacious in preventing relapse to opioid dependence provided that it is taken as prescribed, but adherence with oral naltrexone is problematic and leads to extremely high dropout rates, with the occasional exception of treatment in criminal justice and other settings where relapse may be linked to severe adverse consequences [96-98]. This has led to intensive efforts – including NIDA- and NIAAA-funded grants to small businesses – to develop long-acting naltrexone preparations that can be administered as an injection or placed as an implant once per month or less frequently [99, 100].

XR-NTX (Vivitrol®, NTX-containing polylactide-co-glycolide [PLG] biodegradable sterile microspheres suspended in a diluent) is delivered by monthly injection into the muscles of the upper outer quadrant of the buttock. Each vial of microspheres contains 380 mg NTX which are suspended by adding a diluent that comes with the product and shaking for about a minute prior to injection of the full (less dead-space) content of the vial. Plasma concentrations of NTX and 6-beta-naltrexol (its main active metabolite) after a single XR-NTX injection are detectable for at least 30 days. Consistent with this, in human laboratory studies with Vivitrol® and Depotrex®, an essentially complete blockade of opioid agonist effects is seen for 30 days [101, 102]. To maintain blockade beyond 30 days, XR-NTX must be re-administered. Long-term use of NTX and XR-NTX is not associated with tolerance, dependence, addiction or withdrawal on discontinuation. NTX and XR-NTX will, however, precipitate withdrawal in individuals physiologically dependent on opioids and decrease opioid tolerance.

As a consequence of its extended duration of action and assured treatment adherence, XR-NTX may dramatically and favorably alter the limited effectiveness profile associated with orally administered NTX. By ensuring 30-day medication adherence with a single injection, and thereby establishing a ~30 day mu-opioid antagonist blockade, the likelihood of an individual re-establishing opioid dependence during this period is very low. Two clinical trials support efficacy for XR-NTX preparations compared to placebo injections [54, 55].

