24.2.5.5 Study Specific Risks

XR-NTX blocks the effects of exogenous opioids after administration. After treatment, participants are likely to have reduced tolerance to opioids. Following Vivitrol® treatment, opioid use at the end of a dosing interval or after missing a dose could result in potentially life-threatening opioid intoxication (involving respiratory compromise or arrest, circulatory collapse, etc.) Attempting to overcome the blockade effects of Vivitrol® by administering large amounts of exogenous opioids is associated with potential risk of opioid overdose. Participants in this study will receive an information card that will notify clinicians that they are receiving XR-NTX as part of a research study.

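### Sections 4.2 and 9.2.3.3 give different durations of XR-NTX blockade (30 days and 5 weeks), and the 7-day grace period with its no-relapse-risk wording rests on the longer one

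*Combined protocol and SAP*

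**What the plan says.** Four places in the combined protocol and SAP bear on how long an injection works and what a late one means.

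- **Section 4.2 (drug background).** It reports that "an essentially complete blockade of opioid agonist effects is seen for 30 days [101, 102"], and the next sentence is "To maintain blockade beyond 30 days, XR-NTX must be re-administered". It later repeats a blockade of about 30 days and calls renewed dependence in that period very unlikely, not impossible.
- **Section 9.2.3.2 (dosing).** Injections are given about every four weeks: "treatment initiation visit and weeks 4, 8, 12, 16, and 20".
- **Section 9.2.3.3 (missed doses).** It gives "full blockade out to 5 weeks after the last injection", citing reference 101, and places partial blockade only after week 5. From this it concludes that "a grace period of at least 7 days after the scheduled injection can be expected". For an injection given late but inside that window it makes an absolute claim, namely that "repeat XR-NTX injection can be rescheduled without risk of relapse". The next sentence tells the provider to suspect relapse, and to repeat the naloxone challenge, if the participant misses the injection and uses opioids on two or more of the seven days after the scheduled date. The section also ranks a missed injection as the chief danger to naltrexone maintenance.
- **Section 24.2.5.5 (Appendix B, risks).** It warns that "opioid use at the end of a dosing interval or after missing a dose could result in potentially life-threatening opioid intoxication".

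The synopsis (Section 2.0) adds a shorter figure, "a deep muscle injection that lasts 28 days, eliminates the need for daily dosing", but this describes the injection in general and not blockade as such.

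**The concern.** Section 9.2.3.3 is the protocol text that sites have for missed doses. Its grace period is derived from a blockade duration that the drug-background section does not support, although reference 101 is cited for both figures. A site reading Section 4.2 and a site reading Section 9.2.3.3 could therefore differ on whether a participant in the fifth week after an injection is still fully blocked.

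The no-risk phrase makes this worse because it is absolute. Nothing else in the protocol supports a complete absence of relapse risk in that week, and the surrounding text is written on the footing that relapse can occur then. At stake are the consistency and safety of missed-dose handling in the XR-NTX arm.

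**Working it through.** The check is day arithmetic, counting the day of an injection as day 0.

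**Inputs**

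- Dosing interval: 4 weeks = 28 days (Section 9.2.3.2).
- Full blockade: 5 weeks = 35 days (Section 9.2.3.3).
- Essentially complete blockade: 30 days (Section 4.2).
- Duration of the injection: 28 days (Section 2.0).
- Grace period: at least 7 days after the scheduled date, that is days 29 to 35 (Section 9.2.3.3).

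**Formula:** margin = stated duration − dosing interval.

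| Source of duration | Duration (days) | Margin after day 28 (days) | Grace days outside the stated duration |
|---|---|---|---|
| Section 9.2.3.3 | 35 | 35 − 28 = 7 | 0 of 7 |
| Section 4.2 | 30 | 30 − 28 = 2 | 5 of 7 (days 31 to 35) |
| Section 2.0, not a blockade figure | 28 | 28 − 28 = 0 | 7 of 7 |

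The first row reproduces the protocol's own 7 days. Neither shorter figure does. The two blockade durations differ by 35 − 30 = 5 days. These rows show the size of the disagreement; none is offered as a rule.

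**The no-risk wording against the rest of Section 9.2.3.3.** The grace period and the relapse rule cover the same seven days. One sentence says an injection can be moved within them with no relapse risk. The next defines when relapse is to be suspected within them. Both cannot hold as written, and this conflict remains whichever duration is correct.

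**Exposure.** There are six scheduled doses: initiation plus weeks 4, 8, 12, 16 and 20. The first cannot be late in this sense, and no study dose follows the sixth. So at most 6 − 1 = 5 repeat injections per participant can fall in the disputed window, and only among those who start XR-NTX. The documents give no rate of late injections, so no expected number can be calculated.

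**The case against.** **The 30 days may be a minimum.** The Section 4.2 statement covers two products and cites references 101 and 102, while Section 9.2.3.3 cites 101 alone. Thirty days might be the period common to both products, or the length of observation. The sources are not available here, so this cannot be excluded, and the shared citation is weaker evidence than it first looks. But the following sentence in Section 4.2, on re-administration beyond 30 days, reads as a limit. The mismatch stands.

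**Sites are not told to relax.** Section 9.2.3.3 has staff contact the participant and rebook promptly. The challenge trigger runs from the scheduled date and does not wait for day 30 or day 35. Restarting an abstinent participant up to 3 weeks late requires no reported use, a negative urine and a passed challenge. Urine drug screens are taken at every 4-weekly visit (Section 14.1). This stands, and it limits the harm. It does not remove the conflicting durations or the no-risk statement.

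**Stronger readings the documents do not support**

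- A reader might infer that Section 24.2.5.5 flatly contradicts the no-risk phrase. It does not: it concerns overdose after opioid use with reduced tolerance, and the phrase concerns relapse. The two sit uneasily together, and Section 9.2.3.3 does not refer to the warning, but that is less than a contradiction.
- A reader might infer that participants are unprotected on days 31 to 35 and that sites would wrongly treat them as protected. Section 4.2 does not say protection is absent then, Section 9.2.3.3 describes partial blockade even after week 5, and its instructions are to rebook and monitor.
- A reader might multiply 175 participants by 6 injections to get 1,050 exposures. That is not an estimate. At most five repeat injections can be late, and not everyone will start: in the pilot 5 of 12 participants with opioid use disorder began XR-NTX within 4 weeks (Section 4.3), although this trial aims to raise that share and allows initiation until week 20.

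**Conclusion.** The inconsistency is real and should be corrected. The protocol states two durations of blockade, 5 days apart, and its grace period follows only from the longer. On the shorter, 5 of the 7 grace days fall outside the stated blockade. Separately, the no-risk wording conflicts with the relapse rule and the emphasis on missed injections in the same section.

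The conclusion rests on two assumptions: that the interval is 28 days, as scheduled, and that the 30 days in Section 4.2 is a limit, which its next sentence supports. The conflict within Section 9.2.3.3 needs neither.

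The practical reach is modest: late repeat injections only, at an unknown rate, with rebooking and challenge procedures already in place. No endpoint, margin, error rate, power or sample size depends on it. The documents do not settle which duration is correct, and no view is taken here.

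**What to change.** Reconcile Sections 4.2, 9.2.3.3 and 24.2.5.5 so that one duration of blockade is stated with its source, and check the synopsis figure against it. Then make the grace-period, missed-dose and naloxone-challenge wording agree with that duration and with one another. The no-relapse-risk phrase should be included in that revision, and Section 9.2.3.3 should refer to the overdose warning in Appendix B. The challenge procedure in the Manual of Operating Procedures, which is not among the documents, should be checked for the same point.

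The choice of duration and of missed-dose rule belongs to the clinical team, working from the package insert and the cited sources.

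The cost is protocol wording, submitted as an amendment in the usual way, and a note to sites. The reconciliation itself adds no procedures, visits or data collection.
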